Results: Dually diagnosed veterans reported significantly more craving for alcohol when exposed to trauma imagery than when exposed to stressful or neutral imagery ($p<0.001$) (Figure 1). The stress response decreased with treatment, and those with high stress response on prazosin reported greater, but not statistically significant, change in their drinking at the end of treatment (Figure 2). Also, there was a significant relationship ($r=0.603$) (Figure 3) between craving and the number of drinking days at follow up.

Conclusions: The preliminary findings show that veterans with dual diagnosis report strong craving after exposure to trauma

related imagery. **Based on this result we eliminated the stress condition for the present study.** The trauma-induced response predicted drinking at the end of treatment and at follow up.

- *These finding support the notion that reactivity to stress may increase the susceptibility for relapse.*
- *This study demonstrates that we have experience with this paradigm.*
- *It validates the ability of our research team to recruit individuals with AUD and PTSD.*

4. Significance:

To our knowledge, this study is the first to examine the ability of progesterone to reduce trauma or stress-induced craving in individuals diagnosed with a) comorbid AUD and PTSD and b) AUD only. Positive findings from this study will: 1) provide evidence that progesterone is important in mediating stress and alcohol craving, 2) provide insight into the underlying mechanisms of stress and alcohol craving, 3) help identify a potential marker that will distinguish who may be at

higher risk for alcohol relapse, and 4) provide a platform for other exploratory studies that can include the use of progesterone as treatment options for AUD and PTSD.

5. Research Plan:

Participants: Participants (N=72 completers) will be eligible for the study if they fullfill the following criteria:

Inclusion criteria:

- a) men (n=36) and women (n=36) age 21 to 60;
- b) have current diagnosis of *either*:
 - 1. AUD and comorbid PTSD
 - OR
 - 2. AUD

AUD will be determined by Structured Clinical Interview for DSM-5 (SCID-5) (First, Spitzer, Gibbon, & Williams, 2015). PTSD will be determined by Clinician Administered PTSD scale (CAPS-5)(Weathers et al., 2013) and by SCID-5);

- c) drink regularly (determined by TLFB and recorded 90 days prior to the interview);
- d) are not in an active phase of alcohol withdrawal;

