- e) are not at risk for suicide; if on medication, they must be on a stable dose for at least 2 weeks;
- f) for women, have regular menses every 25-35 days.

Exclusion Criteria:

- a) current SCID diagnosis of any psychotic disorder; substance use disorder (other than alcohol, nicotine, and marijuana) in the past 30 days;
- b) current unstable medical condition; positive test results at more than one baseline appointment on urine drug screens conducted for opiates, cocaine, benzodiazepines, and barbiturates (marijuana is allowed);
- c) for women, amenorrhea, use of oral contraceptives;
- d) known allergy to progesterone or peanuts (vehicle for micronized progesterone);
- e) history of thrombophlebitis, deep vein thrombosis, pulmonary embolus, clotting or bleeding disorders, heart disease, or history of stroke.

Methods: All participants will complete 1 test day. In order to control for gender differences in progesterone levels we will test women in the follicular phase of the menstrual cycle. This experiment is a between-subject design. Before the test day every participant will receive either progesterone (200 mg. bid) or placebo in identical looking capsules for three days. In previous studies with addicted individuals, this dosing schedule of progesterone attenuated stress-induced craving and improved cognitive function(Fox et al., 2013; Sofuooglu et al., 2011). On the fourth day they will attend the laboratory session. The study will consist of four phases. 1) We will first recruit participants, obtain informed consent, and evaluate eligibility for the study. 2) Following completion of intake assessments, participants will receive a full physical examination to further determine eligibility. 3) If eligible they will be randomized to start pre-treatment with either progesterone or placebo and scheduled for the laboratory session. 4) Follow-up: Participants will be contacted approximately 1 day after completing the stress lab to see how they are doing and to answer questions about their drinking. They will also be asked to come for one follow up session 1 month later to determine their drinking habits following the lab session.

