Medication: All participants will be asked to take progesterone or placebo for three days leading up to the laboratory test day. They will be asked to take the first dose of medication

(progesterone or placebo) at night to minimize possible sedation from progesterone treatment. The following morning they will come to the clinic to take the second dose in the morning and will be given three additional doses (one to take at night the same day and two doses – morning and night for the following day). On the fourth day they will come in the morning for the laboratory session and will take one last dose in the lab. For women, the treatment will be initiated within the first 4 days of the menstrual cycle, day one being the first day of menses, and will be completed within the early follicular phase.

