Laboratory sessions: Laboratory sessions will be conducted on the Biological Studies Unit at the West Haven VA with trained personnel, and a psychologist or MD will be on call during the laboratory session. Additionally, all participants will be cleared by a study doctor prior to leaving the lab at the end of the imagery session (see Table 1 for details). Participants will be asked to arrive around 10:00 am. On arrival there will be a urine and breath alcohol concentration (BrAC) check. If clear to start an IV line will be placed. Those who test positive for any substance (other than marijuana) will be discharged. Blood pressure and pulse will be monitored continuously. Subjective measures of craving for alcohol, anxiety, affect, and cognitive functioning will be administered shortly after the set up. Prior to the presentation of the 1st and 2nd tapes, the relaxation technique will be used. Two conditions will be administered in a counterbalanced order: Trauma/Stress script and Neutral script. Subjective measures of craving, anxiety, affect, and cognitive functioning will be presented:1) prior to presentation of the scripts, b) immediately after presentation of each script, and c) following a 5 minute recovery period. After the last recovery period and assessments subjects will be encouraged to use the relaxation techniques. Craving and emotional distress will be evaluated throughout the session and subjects must return to baseline levels prior to being discharged from the unit. Subjects will wear an ambulatory physiological monitor (APM) (Eqvital EQ02, Vivonoetics, San Diego, CA) that collects continuous ECG, respiration, and activity for 20 minutes while at quiet rest at baseline, and throughout the stress challenge procedure. After completion of the scheduled portion of a session, any subject that reports residual craving or distress will participate in guided relaxation procedures with a clinically-trained psychologist for up to one additional hour. Relaxation has also been shown to reduce PTSD symptoms(Hamid & Neissi, 2009). If craving or emotional distress persists after an hour of relaxation training, the subject will receive an individual counseling session with a psychologist who is experienced in psychotherapy for PTSD. If craving or emotional distress persists after the psychotherapy session, the subject will be escorted to the Emergency Department and treated by the on-call psychiatrist.

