Progesterone, a natural hormone, is safe and well-tolerated by women. The safety, tolerability and efficacy of micronized progesterone is well established and it is FDA approved for hormone replacement therapy (HRT), absence of menstrual periods (amenorrhea), and infertility treatment. The recommended dose of progesterone for hormone replacement treatment is 200 to 400 mg/day, given as a single evening dose. After oral administration, micronized progesterone reaches its peak plasma levels in two to three hours and has an elimination half-life of three to four hours (McAuley *et al*, 1996). Because of its short half-life progesterone will be given twice daily to maintain stable plasma levels. Progesterone doses higher than 400 mg/day will not be used since they are more likely to cause sedation. The safety and tolerability of micronized progesterone are well established. Others have used micronized progesterone in several previous studies with male and female smokers and cocaine users (Sofuooglu *et al*, 2001; Sofuooglu *et al*, 2009; Sofuooglu *et al*, 2011). Progesterone was well-tolerated and there were no serious adverse events. The most common adverse effect is mild sedation. Other less common adverse effects include menstrual irregularity, spotting or breakthrough bleeding, dizziness, cramps, nausea, fatigue, headache, an allergic reaction, and breast tenderness. Other side effects attributed to synthetic progestin, including depression, fluid retention, pruritus, jaundice, rash and thrombotic disorders have not been observed with natural progesterone. Women will be warned to use caution when driving a motor vehicle or operating machinery while undergoing study treatment.

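### The only driving and machinery caution in the protocol is addressed to women, although men take the same progesterone regimen

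*Combined protocol and SAP*

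**What the plan says.** The caution is in section 5 (Research Plan), under Progesterone: "Women will be warned to use caution when driving a motor vehicle or operating machinery while undergoing study treatment". It is the only sentence in the visible text about driving or machinery.

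The trial enrols both sexes in equal numbers, "men (n=36) and women (n=36) age 21 to 60" (Inclusion criteria), and the regimen does not differ by sex: "Before the test day every participant will receive either progesterone (200 mg. bid) or placebo in identical looking capsules for three days" (Methods).

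Sedation comes up in three places:

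- **Progesterone.** The dose is capped: "Progesterone doses higher than 400 mg/day will not be used since they are more likely to cause sedation". A little later the text says "Others have used micronized progesterone in several previous studies with male and female smokers and cocaine users", and soon after that it names mild sedation as the most common adverse effect.
- **Medication.** All participants take the first dose "at night to minimize possible sedation from progesterone treatment".
- **Progesterone effects in men.** Treatment is described as well tolerated in men, with sedation as the principal side effect at higher doses. The male studies cited there used from 200 mg to over 1,500 mg a day.

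**The concern.** A driving caution exists because of sedation, and the protocol treats sedation as possible in anyone taking the study dose. Addressing the caution to women alone leaves out half the planned sample, and no reason is given.

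The restriction reads literally. When the thrombotic and cardiovascular risks are discussed in the same part of section 5, the warning is addressed to subjects in general. Staff who follow the text as written would give the driving advice to women and not to men.

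What is at stake is a cheap precaution for participants. Neither the comparison of progesterone with placebo nor the sample size is affected.

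**Working it through.** The plan states no figure to reproduce. The check sets the relevant statements side by side and counts doses.

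**1. Daily dose against the sedation ceiling.** Methods gives 200 mg twice daily. 2 × 200 mg = 400 mg/day on each full dosing day. The Progesterone subsection rules out doses above 400 mg/day because of sedation. Both sexes are therefore dosed exactly at the ceiling.

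**2. Share of the sample.** Inclusion criteria plan 36 men among 72 completers: 36/72 = 50%. The capsules look identical, so the caution has to be given to every man whatever his allocation.

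**3. Dose schedule.** The Medication subsection gives a night dose first. It then says "The following morning they will come to the clinic to take the second dose in the morning and will be given three additional doses": one for that night and two for the next day. A last dose is taken in the laboratory.

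| Dose | When | Where | Doctor's clearance stated afterwards? |
|---|---|---|---|
| 1 | Day 1, night | Home | No |
| 2 | Day 2, morning | Clinic | No |
| 3 | Day 2, night | Home | No |
| 4 | Day 3, morning | Home | No |
| 5 | Day 3, night | Home | No |
| 6 | Day 4, morning | Laboratory | Yes |

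Total: 1 + 1 + 3 + 1 = 6 doses, 3 at night and 3 in the morning. The clearance is the one in Laboratory sessions: "all participants will be cleared by a study doctor prior to leaving the lab at the end of the imagery session". It covers 1 of the 3 morning doses and leaves 2 without one.

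**4. When the effect would be felt.** The Progesterone subsection puts peak plasma level two to three hours after an oral dose.

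- Day 4: Table 1 lists the dose in the block starting at about 10:00 am. If it is taken then, the peak falls at about 12:00 to 1:00 pm, and the last measures start at about 2:15 pm. The participant is still on site.
- Day 2: the dose is taken in the clinic, but the length of the visit is not stated, so the peak may come after the participant has left.
- Day 3: the dose is taken at home, and the peak falls in ordinary daytime with no staff present. This is the only unsupervised morning dose.

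**5. Does any other safeguard do the same job?** Four apply to both sexes: the dose ceiling, the night-time first dose, the Side Effects Questionnaire and the laboratory-day clearance. The first two reduce sedation. The questionnaire is completed before randomization, at the medication visit and before the laboratory session; it records effects, and no driving advice is attached to it. The clearance covers day 4 only. None of the four is a driving caution.

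**The case against.** The strongest reply is that participants are warned through the consent form and medication instructions. Consent pages were removed from the public file and cannot be counted as missing. This stands: nothing here shows that any man goes unwarned, and the finding is limited to the protocol sentence.

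Second, the Progesterone subsection can be read as mainly about women. It opens with tolerability in women and lists menstrual effects, while men have their own subsection, which ties sedation to higher doses. This has some force, but it does not remove the point. The sedation statement closely follows a reference to male and female users. The subsection on men gives no dose threshold and cites studies starting at 200 mg a day. The night-time first dose, adopted because of sedation, applies to everyone.

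Third, the remaining risk is small: the effect is called mild, only six doses are taken, and the safeguards above cover both sexes. That is right, and it is why the point is minor.

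Fourth, the counts have limits. The 36 are planned completers, so if some men drop out after dosing, more than 36 will have been dosed. Only men on progesterone are exposed to the drug, and the allocation ratio is not stated. The day 2 dose involves clinic contact, so day 3 is the clearest gap. None of the counts estimates the chance of a driving event.

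**Conclusion.** The concern holds as a matter of protocol wording. The only visible driving and machinery caution is limited to women. Men, half the planned completers, take the same 400 mg/day, at the ceiling set because of sedation, and no reason for the restriction is given. Two of the three morning doses have no stated doctor's clearance, and one of those is taken at home.

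This rests on two readings: that the sedation statement is not confined to women, and that the reference to higher doses in the subsection on men does not exempt them at 400 mg/day. Whether men are warned in practice cannot be judged from the public file. The wording may simply have carried over from text written about women. It should be corrected, but it is a minor participant-safety point with no bearing on sample size, power or analysis.

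**What to change.** In the Progesterone subsection of section 5, change the subject of the sentence so that it reads *All participants will be warned*, leaving the rest as it stands. Then confirm that the consent form and the medication instructions given with the take-home doses carry the same caution for both sexes; they may already do so.

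The cost is one changed subject in one sentence and a check of two documents. No procedure or visit changes.

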Initial Assessments: Participants will be interviewed with the SCID and CAPS for diagnostic evaluation. The TLFB(Sobell & Sobell, 1992) will be used to document the degree of daily alcohol consumption in the three months prior to study entry. Participants will have a psychiatric and medical examination by one of the investigators. Study data will be collected and managed using REDCap electronic data capture tools hosted at VA CT Healthcare System. REDCap

(Research Electronic Data Capture) is a secure, web-based application designed to support data capture for research studies, providing 1) an intuitive interface for validated data entry; 2) audit trails for tracking data manipulation and export procedures; 3) automated export procedures for seamless data downloads to common statistical packages; and 4) procedures for importing data from external sources (Harris et al 2009).

Screening and Baseline: Each participant will sign an informed consent. The study will be conducted with the approval of the VA Connecticut Human Subject Subcommittee. As part of the screening procedure detailed clinical assessment (to determine diagnosis), and medical assessments (physical exam, medical history, blood work and electrocardiogram) will be conducted. Those participants who fulfill all the inclusion and exclusion criteria will be enrolled in the study. On the first visit participants will be asked to come for a script development session. Also, women will be instructed to call the clinic when their menses starts and begin taking the study medication within the first 4 days of their menstrual cycle. The procedure is implemented in order to give some flexibility to female subjects and to ensure that they can finish the study during the early follicular phase (within the first seven days of the menstrual cycle).

Script Development Session: Scripts will be developed during a visit prior to the first laboratory session. Two scripts will be developed for each participant based on a procedure developed by our group. Participants with AUD and comorbid PTSD will develop one trauma related script and one neutral script. Participants with AUD only will develop one stress related script (since they have not experienced trauma) and one neutral script.

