There is black-box warning for progesterone regarding the risk for cardiovascular disorders and breast cancer. The black box warning mentions the Women's Health Initiative (WHI) study in which treatment of postmenopausal women (50 to 79 years of age) with daily oral conjugated estrogens combined with medroxyprogesterone acetate (MPA), relative to placebo, reported increased risks of deep vein thrombosis, pulmonary embolism, stroke, and myocardial infarction (Hammond, 2005). The pharmacological effects of MPA, a progestin, differ significantly from those of progesterone. MPA, but not progesterone, has well-characterized androgenic, glucocorticoid and anabolic effects and have been associated with unfavorable side effects including fluid retention, androgenic effects, alterations in lipid profile, increase risk for breast cancer (Fournier *et al*, 2008; Fournier *et al*, 2005), and cardiovascular events (Hermsmeyer *et al*, 2008). In contrast to MPA, progesterone is not known to cause these adverse events (Fournier *et al*, 2008; Fournier *et al*, 2005; Hermsmeyer *et al*, 2008). However, as a safety measure for these serious adverse events, we will exclude subjects with history of thrombophlebitis, deep vein thrombosis, pulmonary embolus, clotting or bleeding disorders, heart disease, or history of stroke, breast cancer or other cancers. Subjects will be

warned about these side effects and the physician will be alerted to the earliest manifestations of thrombotic disorders including thrombophlebitis, cerebrovascular disorders, pulmonary embolism, and retinal thrombosis. If any of these occur or be suspected, the study medication will be discontinued immediately. In previous studies conducted in the VA CT Healthcare System, micronized progesterone was well tolerated by both male and female cigarette smokers and cocaine users. Subjects will complete a questionnaire to note any important side-effects using the Side Effects Questionnaire (SEQ) prior to randomization (baseline), at the medication visit, and prior to the start of the laboratory session.

Progesterone effects in men: In contrast to the cyclic changes in progesterone levels in normally menstruating women, men have steady levels of plasma progesterone. The physiological levels of plasma progesterone in men are similar to the follicular phase progesterone levels found in women (Zumoff et al., 1990).

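### The safety text excludes people with a history of breast or other cancers, but the exclusion list omits cancer, so past or stable cancer passes the listed criteria

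*Combined protocol and SAP*

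**What the plan says.** Two current parts of section 5 (Research Plan) of the combined protocol and SAP state who is excluded on medical-history grounds.

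- **Exclusion Criteria, item e):** "e) history of thrombophlebitis, deep vein thrombosis, pulmonary embolus, clotting or bleeding disorders, heart disease, or history of stroke". The item ends there.
- **Progesterone, boxed-warning paragraph:** "However, as a safety measure for these serious adverse events, we will exclude subjects with history of thrombophlebitis". The sentence then continues through the same conditions and closes with "heart disease, or history of stroke, breast cancer or other cancers".

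The nearest other listed criterion is b), which begins with "current unstable medical condition" and then turns to urine drug screens.

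On how eligibility is decided, the Participants paragraph makes it turn on the criteria that follow it, and Screening and Baseline enrols those who meet all inclusion and exclusion criteria. Screening itself is thorough. Under Methods, "participants will receive a full physical examination to further determine eligibility". Under Initial Assessments, "Participants will have a psychiatric and medical examination by one of the investigators". Under Screening and Baseline, "medical assessments (physical exam, medical history, blood work and electrocardiogram) will be conducted".

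**The concern.** The boxed warning that the protocol cites concerns cardiovascular disorders and breast cancer. The sponsor answered it with a set of exclusions, but only the vascular, clotting, cardiac and stroke items reached the list that decides enrolment.

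The examination, medical history and blood work should bring a cancer history to an investigator's attention. The listed criteria then give that investigator no rule to apply. Exclusion depends on knowing a sentence several pages further on, in the description of the drug. A person with past or stable cancer could be randomised against the protocol's own commitment, and two members of staff could decide the same case differently.

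**Working it through.** The main check is a comparison of texts; the plan states no figure on this point to reproduce.

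**1. The two lists side by side.** I count clotting or bleeding disorders as one item, and breast cancer and other cancers as two.

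| History of | Progesterone subsection | Exclusion criterion e) |
|---|---|---|
| Thrombophlebitis | yes | yes |
| Deep vein thrombosis | yes | yes |
| Pulmonary embolus | yes | yes |
| Clotting or bleeding disorders | yes | yes |
| Heart disease | yes | yes |
| Stroke | yes | yes |
| Breast cancer | yes | **no** |
| Other cancers | yes | **no** |

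The lists hold 8 and 6 items, so 8 − 6 = 2 are missing. Criterion e) closes with a full stop after stroke, so nothing suggests redaction or text lost in extraction. Neither place is an amendment log.

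**2. Whether another criterion closes the gap.** Criteria a), c) and d) cover psychiatric and substance use diagnoses, menstrual and contraceptive status, and allergy. Criterion b) requires a condition to be both current and unstable. It could stop active, unstable cancer, but it does not reach past or stable cancer. Cancer is named in no eligibility criterion, and nowhere outside the boxed-warning paragraph.

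**3. Exposure of a wrongly enrolled person in the progesterone arm.** The Medication paragraph gives one dose on the first night, one in the clinic the next morning, three to take away, and a last one on the laboratory day: "On the fourth day they will come in the morning for the laboratory session and will take one last dose in the lab".

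- Doses: 1 + 1 + 3 + 1 = 6
- Total: 6 × 200 mg = 1,200 mg
- Daily maximum: 2 × 200 mg = 400 mg, within the 200 to 400 mg/day that the Progesterone subsection gives for hormone replacement

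**4. Number of people concerned.** The documents give no prevalence of cancer history. I assume 1% to 5%, purely for scale, and apply it to the 72 planned completers.

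- 72 × 0.01 = 0.72, about 0.7
- 72 × 0.05 = 3.6

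These figures cover both arms and suppose that nobody is stopped at screening, so they are upper bounds for the assumed prevalence. With equal allocation, which is also an assumption because no ratio is stated, the number receiving progesterone would be half: 0.72 / 2 = 0.36, about 0.4, to 3.6 / 2 = 1.8.

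**The case against.** The strongest reply is that the rule already exists. The Progesterone subsection is part of the Research Plan, not of the Background section, and the same paragraph holds other working instructions, such as stopping medication if a thrombotic disorder is suspected and when to complete the side-effects questionnaire. Criterion e) does not say that people with cancer may enrol, so staff can obey both texts by excluding them. No document says that screening uses the lettered list alone. An investigator examines every participant, and the absence of a checklist from this document does not show that none exists. The dose is modest and brief, and the paragraph itself says that progesterone, unlike the synthetic progestin in the cited trial, is not known to carry these harms. On this view the mismatch is a minor editorial matter.

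Much of this stands. The intent is on record, the clinical risk is limited, and the assumed prevalence gives an upper bound only. What does not follow is that the list can stay as it is. The six companion items were placed there, so a screener may reasonably take it as complete. The examination can reveal a cancer history, but the list does not say what to do with it. And the sponsor chose the exclusion despite stating that progesterone is not known to cause these events, so low risk is not a reason to leave the sponsor's own precaution out of the operative criteria.

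**Conclusion.** The concern holds. The eligibility list, applied as written, admits people with past or stable cancer whom the same protocol says it will exclude. Two of eight safety exclusions are missing, and no other criterion replaces them.

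The practical size is small: a person wrongly enrolled in the progesterone arm would take 1,200 mg over six doses, and few people are likely to be concerned. The head count rests on the assumed 1% to 5% prevalence and on no one being stopped at screening; the textual finding rests on neither. How sites screen in practice is unknown. Nothing here touches power, alpha or the analysis. It should be fixed because it concerns a safety exclusion that the protocol ties to a boxed warning.

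**What to change.** Extend exclusion criterion e) to cover a history of breast cancer or other cancers, so that it matches the Progesterone subsection. Align any eligibility checklist and the medical-history screen with the amended criterion. If participants have already been enrolled, check their recorded medical histories against it.

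The cost is a one-line amendment, plus a checklist update if there is a checklist. Under the assumed prevalence, about 1 to 4 people per 72 would become ineligible under the list, all of whom the protocol already says should not enter.
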